#### **Eligibility Criteria:**

The inclusion criteria are:

- Male and female patients 18 years of age or older
- Orthopaedic trauma patients with an isolated injury requiring surgery
- Informed consent obtained
- Working cellphone

The exclusion criteria are:

- Enrolled in a study that does not permit co-enrollment
- Unlikely to comply with the follow-up schedule
- Unable to converse, read or write English at elementary school level
- Unlikely to complete surveys at home, access to phone
- Incarcerated
- Pregnant
- COVID positive

Patients will be free to withdraw from the study at any time, for any reason.

A patient may also be withdrawn/removed by the study team, if necessary, to protect the patient's health. Once a patient withdraws, the reason will be documented.

#### **Informed Consent Process:**

Consent will be obtained via REDCap after a thorough consent process and after patients have been given the opportunity to answer any questions. Patients will read the consent form first, and then the explanation will be given. Finally, patients will be asked if they would like to participate. Patients will be allowed to take a copy of the consent with them if they require more time.

#### **Compensation for time and effort:**

Both intervention and control participants will receive compensation at the following visits:

- Enrollment / Hospitalization gift bag and a \$10 gift card
- 2 week \$20 gift card
- 3 month \$20 gift card

#### **Data and Safety Monitoring and Reporting:**

The Life Care Specialist (LCS) and/or study personnel will respond to study patients to employ behavioral and non-pharmacologic strategies that are designed to decrease opioid utilization, improve pain control via alternative techniques, and educate patient on pain management. Enrolled patients will receive support, direct connection to resources, and follow-up with the LCS during their participation in the program. The patients enrolled in the intervention arm of the RCT will receive direct support and regular follow up with the LCS in obtaining necessary services and ensuring an appropriate level of education is met.

There will be no direct intervention other than education, mentoring, and advocacy on behalf of the patient by study personnel therefore minimizing risk of misusing prescriptions.

#### **Confidentiality:**

The Life Care Specialist and the study personnel will ensure that the patient's anonymity is maintained, and that the patient identity is protected from unauthorized parties. The patients will have a designated identification code rather than being identified by their names. All study files and documents will be locked in file cabinets and accessible only to the study personnel.

Though study participants will be using pain medications as prescribed, the investigators acknowledge that participants are asked to quantify their consumption of a controlled substance, which may be a sensitive matter for some participants. Thus, in order to further protect the confidentiality of participants' responses to survey questions and online survey responses will be stored as a set of numbers only, without identifying the question to which those numbers pertain. This data will be stored in an encrypted fashion on a commercial cloud server, which is password protected and only accessible by Emory research staff. The survey key linking the questions to the patient responses will also only be available to Emory investigators.

#### **Statistical Analysis:**

**Aim 1:** Examine differences in post-surgical patient-reported pain related outcomes between those in the intervention compared to the control arm. A multivariable mixed effects logistic regression model will be constructed to test the hypothesis that participants in the intervention arm have lower average NRS pain scores and PROMIS scores postoperatively compared to participants in the control arm. A separate linear mixed effects model will be constructed for each outcome. This modeling approach will enable the team to examine the mean differences in each patient-reported pain related outcome while adjusting for covariates (e.g., mental health history, BMI, surgery type, etc.).  The mixed effects modeling will account for potential collinearity between participants seen by the same surgeon by fitting a random effect for both factors. Models will be constructed using a Least Absolute Shrinkage and Selection Operator (LASSO) method. 50,51 An extension of traditional ordinary least squares regression model building, LASSO is a machine learning method capable of balancing bias and variance to build the most predictive model with a large subset of covarying factors using a penalized approach. A LASSO approach enables the team to systematically evaluate the variance introduced into regression modeling by hundreds of potential confounders. This unique quantitative capability will allow the research team to exploit the hundreds of data points collected from the electronic health records and the patient-reported outcomes collected per participant. The inclusion of these longitudinal measures makes it feasible to reduce statistical variation in the mixed effects models over time and therefore isolate the effect of the intervention. The fit of the most appropriate and still parsimonious model produced by the LASSO will be assessed based on the AIC score.

Aim 2: Evaluate the effectiveness of Life Care Specialist intervention on reducing long-term postoperative opioid medication utilization. As described above, a systematic machine learning guided model construction approach will be used to also test the working hypothesis that participants in the intervention will report decreased utilization of opioid pain medications both in the inpatient and outpatient setting up to 3-months postoperatively. Separate mixed-effects models will be constructed to estimate differences in average MME/day during inpatient hospitalization as well as to estimate difference in average MME/day over every study follow up point up to 3-months postoperatively.

Aim 3: Explore the feasibility of utilizing actigraphy devices to capture postoperative functional outcomes among patients during their hospitalization and up to 2-weeks postoperatively following orthopaedic trauma. Generalized estimating equations (GEE) will be used to explore changes in functional outcomes over the 2-

week postoperative period. For example, activity will be measured as average step per day and sleep will be measured as average nightly sleep efficiency and duration. Separate GEE will be computed for each actigraphy related measure. In the event a significant change in any of the objective outcomes, a linear mixed-effect model will be constructed to ascertain any significant differences in actigraphy collected outcomes exist between participants in the intervention and the control arms over the two-week postoperative period.

Power: A sample of 200 provides 85% power ( $\alpha$ =0.05) to detect a difference as small as 0.5 in the mean pain score between the intervention arm and the controls using repeated measures mixed effects modeling (Power Analysis and Sample Size Software, NCSS, Kaysville, UT, USA). All analyses will be conducted in R (R Core Team, Vienna, Austria) by the Co-PI and his team at the Nell Hodgson Woodruff School of Nursing ([name]). The *glmnet* package will be used to determine which variables should be included in the regression models using a LASSO approach, the *lme4* package will be employed to compute final regressions and assess fit. Post hoc power analyses will be conducted when exploring differences in outcomes based on demographics (e.g., gender).

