#### **Objectives:**

The overall hypothesis of this pilot randomized-controlled trial is that the introduction of an LCS as a novel member of the clinical care team will help reduce opioid utilization, decrease pain scores, and improve patient understanding of their addiction risk in the aftermath of orthopaedic trauma.

The first aim will evaluate the effectiveness of LCS intervention on pain control and opioid utilization; the second aim will evaluate the effectiveness of LCS intervention on the patient perspective and understanding of their risks; and the final aim will provide early evidence into which patients benefit most from LCS intervention.

All patients will be assessed with a comprehensive social determinants of health survey at the beginning of the study, and follow-up assessments will include actual morphine equivalents utilized (inpatient and outpatient), pain scores (inpatient and outpatient), and substance use surveys up to 1-year post-trauma.

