#### **Study design and methods:**

The pilot trial will include 200 patients – 100 randomized into LCS intervention. Prior to randomization, all patients will be given a standardized, validated, comprehensive social determinants of health assessment.

Patients will be randomized to either:

(1) LCS intervention - With *Opioid Risk Education*, patients will receive opioid education after completing the validated Opioid Risk Tool (ORT), a detailed substance abuse survey and mental health screening, and Naloxone education. *Therapeutic Intervention* will include the Community Resiliency Model CRM), progressive muscle relaxation, sound therapy. *Clinical Pain Coordination* will include directed referrals for complex needs, including mental health and substance use

- disorders, as needed. In addition to above mentioned 3 intervention components, all patients in the LCS intervention arm will also receive the current standard-of-care.
- **(2) No LCS intervention -** Patients will receive the current standard-of-care for pain management in the aftermath of trauma, which includes: a standardized prescription protocol, hospital-system approved discharge instructions which provide written instruction on how to taper opioid use, links to written/online resources for opioid misuse, overdose prevention, and State-approved disposal options.

Patients will be monitored throughout the course of the 1-year study for outcomes. They will also have the same quantity and quality of interaction with their usual clinical providers (orthopaedic trauma surgeon, physician's assistant).

This pilot trial will provide information on the effectiveness of LCS for pain intervention, as well as on study design, retention, effect sizes, and outcomes assessment. Our long-term goals are to determine whether LCSs are beneficial for decreasing opioid risk and improving pain management, and if so identify (1) the key effectiveness factors to the LCS intervention, (2) whether the LCS intervention can decrease overdose-related deaths, and (3) how to scale this model nationally, similar to the Child Life Specialist model.

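### Aims 1 and 2 plan about six or seven between-arm tests with no primary outcome and no multiplicity control: about a 21-30% chance of some false significant difference, and 10-16% of one favouring the LCS

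*Combined protocol and SAP*

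**What the plan says.** The Objectives section gives one overall hypothesis with three parts: the LCS "will help reduce opioid utilization, decrease pain scores, and improve patient understanding of their addiction risk".

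In the Statistical Analysis section, Aim 1 tests whether the intervention arm has "lower average NRS pain scores and PROMIS scores postoperatively compared to participants in the control arm". It then says "A separate linear mixed effects model will be constructed for each outcome". The Study Procedures/Assessments section lists four PROMIS scales: sleep disturbance, physical function, pain interference and prescription pain medication misuse. Aim 1 does not say which of them it means.

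Aim 2 is worded as an evaluation of effectiveness and also tests a hypothesis. It says "Separate mixed-effects models will be constructed to estimate differences in average MME/day during inpatient hospitalization", and it plans the same for MME/day over the follow-up points to 3 months.

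An alpha appears only in the power sentence: "A sample of 200 provides 85% power" at 0.05 to "detect a difference as small as 0.5 in the mean pain score". That sentence gives no instrument, visits or averaging rule for the pain score, and it does not call pain primary. Neither Aim states whether tests are one- or two-sided. No hierarchy, gatekeeping or adjustment is described.

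**The concern.** The trial is called a pilot, but Study design and methods says it will inform on the effectiveness of the LCS, and Aim 2 repeats that purpose. With several hypothesis tests and no ranking, any one significant result could be presented as the trial's result, and the stated 0.05 would govern no overall claim.

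The rest of the text does not supply a primary outcome. The power sentence points to pain. The Introduction and Background gives the main focus as both less opioid use and better pain control. The Objectives section puts pain and opioid use in the same aim. The pain score is itself open: NRS and the DVPRS average-pain item both run from 0 to 10, and both are marked at all four visits in the visit schedule. The NRS row there is labelled as inpatient, and inpatient NRS is recorded daily by clinical staff.

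**Working it through.** **The plan's own figure.** The only stated operating characteristic is 85% power for a 0.5-point difference with 200 patients, "100 randomized into LCS intervention". The SD, the within-patient correlation and the number of repeated measures are not given, so the figure cannot be reproduced. Solving a two-sample comparison backwards, 0.5 / (√(2/100) × (1.960 + 1.036)) gives an SD of the per-patient mean of 1.18. This concerns one test. The plan gives no error rate for the set of tests.

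**Counting the tests (Aims 1 and 2 only).**
- Seven: NRS, four PROMIS scales, inpatient MME/day, follow-up MME/day.
- Six: as above without the PROMIS misuse scale, which is collected only at 3 months and is not clearly a pain outcome.
- Four: NRS, PROMIS pain interference and the two MME/day models.
- Nine: the seven, with follow-up MME/day tested at 2 weeks, 6 weeks and 3 months instead of once.

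The conditional actigraphy models of Aim 3 are left out because that aim is labelled as exploring feasibility. Patient understanding of risk is left out because the Statistical Analysis section gives no model for it.

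**Assumptions.** Each test is two-sided at 0.05. Test statistics are normal with a common correlation ρ, each oriented so that positive means benefit. There is no true effect on any outcome. Any change in per-test error from the LASSO model building is ignored.

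**Formulas for k tests.**
- Independent, either direction: 1 − 0.95^k.
- Independent, favouring the LCS: 1 − 0.975^k, because half of each 0.05 lies on the favourable side.
- Correlated, either direction: 1 − ∫ [Φ((1.96 − √ρ·u)/√(1−ρ)) − Φ((−1.96 − √ρ·u)/√(1−ρ))]^k φ(u) du. For the favourable direction the second Φ term is dropped.

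For example, with k = 7: 1 − 0.6983 = 0.302 and 1 − 0.8376 = 0.162. With k = 6: 1 − 0.7351 = 0.265 and 1 − 0.8591 = 0.141.

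| Tests | Either direction: ρ = 0 | ρ = 0.3 | ρ = 0.5 | Favouring LCS: ρ = 0 | ρ = 0.3 | ρ = 0.5 |
|---|---|---|---|---|---|---|
| 4 | 18.5% | 17.4% | 15.6% | 9.6% | 8.7% | 7.8% |
| 6 | 26.5% | 24.1% | 20.7% | 14.1% | 12.2% | 10.4% |
| 7 | 30.2% | 27.2% | 23.0% | 16.2% | 13.7% | 11.5% |
| 9 | 37.0% | 32.6% | 26.9% | 20.4% | 16.5% | 13.5% |

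The reference for a single test is 5% in either direction and 2.5% favouring the LCS.

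**Sensitivity.** At ρ = 0.7, six and seven tests give 16.4% and 17.8% in either direction, and 8.2% and 8.9% favouring the LCS. If the tests were one-sided at 0.05, seven would give 30.2% (ρ = 0) to 20.3% (ρ = 0.5) favouring the LCS.

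**The case against.** The strongest reply is that this is a pilot. Study design and methods lists retention, effect sizes and design information among its outputs, the Aim 2 hypothesis is called a working one, and the MME/day models are described as estimating differences. The documents never call the tests confirmatory. This tempers the point but does not remove it: the same text speaks of effectiveness, states hypotheses for both aims, and gives power at a stated alpha. If estimation is the real purpose, the plan can say so, and the fix allows for that.

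The objection does stand against four stronger readings that a reader might infer.

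- **That a false claim of benefit has a 23-30% chance.** That range is for seven tests and any significant difference, including one against the LCS. With two-sided tests, the chance of a false result in favour is 11.5-16.2%. Only one-sided 0.05 tests would bring it to 20-30%, and the plan does not state sidedness.
- **That seven is a minimum.** Aim 1 does not list its PROMIS scales. Six and four are both tenable counts, and nine is possible.
- **That every test is set at 0.05.** This is inferred from a single alpha in the power sentence.
- **That NRS averaged over the follow-up visits is the outcome already powered.** The power sentence names neither NRS nor any visits, and DVPRS fits it equally well.

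**Conclusion.** The point holds in a limited form. Aims 1 and 2 set out about six or seven between-arm tests, with no primary outcome and no multiplicity control, in a trial that says it will inform on effectiveness. Under no effect this gives about a 21-30% chance of at least one significant difference in either direction, and about 10-16% for one favouring the LCS. Both are roughly four to six times the single-test rates.

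The figures rest on two-sided 0.05 throughout and on a correlation of 0 to 0.5, neither of which is in the plan. Stronger correlation or a narrower count lowers them, and a wider count raises them. Every count and correlation examined stays well above the single-test rate. For a pilot this is a cheap improvement, not a fatal defect.

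**What to change.** Before analysis, add a short paragraph to the Statistical Analysis section that does the following.

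1. Names one primary outcome with its instrument, visits and summary measure. The natural candidate is the pain score in the power sentence. The sponsor must say whether that is NRS or DVPRS and over which visits, for example the average over the 2-week, 6-week and 3-month visits. Daily inpatient NRS stays separate.
2. Tests that outcome at two-sided 0.05.
3. Lists the PROMIS scales that will be analysed, says whether follow-up MME/day is one test or three, and labels all PROMIS and MME/day outcomes secondary. They are then either Holm-adjusted, or reported as estimates with 95% confidence intervals and no stand-alone effectiveness claim.

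The error for the main claim then returns to 5% (2.5% favouring the LCS). No new data, visits or patients are needed. The price is that a secondary outcome can no longer support a claim by itself at 0.05. With six secondary outcomes under Holm, for instance, the smallest p-value would have to reach 0.05/6 = 0.0083.

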Addiction treatment costs near \$78.5 billion and rising, less than 10% of people in need receive treatment.

According to studies of patients discharged from the hospital after being prescribed a new medication:

- 86% were aware that they had been prescribed new medications.
- Fewer could identify the name (64%) or number (74%) of their new medications of their dosages (56%), the schedule to take them (68%), or the purpose of the prescription (64%.)
- Only 22% could name at least one adverse effect.
- Only 11% could recall being told of any adverse effects.

Further, orthopaedic surgeons are the third-most frequent providers of opioid prescription medications among physicians, and orthopaedic surgical patients are at the highest risk of chronic postoperative opioid use. Orthopaedic trauma surgeons face a very difficult task in managing acute pain and the consequences associated with over-prescription of opioid analgesics. Most patients with orthopaedic trauma injuries have very painful injuries and need appropriate pain control. What we largely fail to understand as providers and then fail to convey to patients is that opioid dependence exists on a continuum: from pain-related appropriate use to dependence – and that addiction can happen to anyone holding a prescription. Orthopaedic trauma surgeons have very little training in acute pain management, yet are treating the highest risk patients with opioids every single day.

Within the orthopaedic trauma population at Grady, 20% of patients report a history of substance abuse, 30% have previously used opioid medications for pain, and nearly 25% report taking opioid pain medications up to 1 year after their trauma (*[name] et al. manuscript in preparation*). Trauma patients are particularly at high risk.

In pediatrics, there is evidence that non-pharmacological interventions by Certified Child Life Specialists (CCLS) has led to more cooperation, reduction in perceived pain, and higher satisfaction scores. The use of CCLS in children who suffer from orthopaedic trauma is associated with fewer opioid prescriptions.

The Christopher Wolf Crusade (CWC) is a 501C3 non-profit providing preventative solutions, education, and advocacy for the American opioid epidemic. Founded by [name] in 2018, CWC is on a mission to save lives worldwide.

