#### VISIT SCHEDULE AND ASSESSMENTS

Assessment	Visit 1:	Visit 2:	Visit 3:	Visit 4:
	Inpatient	2 Weeks (±	6 Weeks (±	3 Months (±
	Hospitalization	7 days)	14 days)	14 days)
Demographics	X			
Trauma registry data	X			
Comprehensive Social Determinants of Health (SDOH) Survey	X			
Revised Opioid Risk Tool (ORT)	X			
Short Form 36 Health Survey Questionnaire (SF-36)	X			X
Pain Management Questionnaire (PMQ)	X	X	X	X
Prescription Drug Use Questionnaire (PDUQ)	X	X	X	X
PTSD Screener	X			X
PROMIS: Sleep Disturbance	X	X	X	X
PROMIS: Physical Function	X	X	X	X
PROMIS: Pain Interference	X	X	X	X
PROMIS: Prescription Pain				X
Medication Misuse				
Opioid Literacy Tool (OLT)	X			X
Patient Satisfaction Survey		X		
Naloxone Questionnaire		X	X	X
PAC-SYM	X	X	X	
Inpatient Opioid Utilization (MME/day)	X			
Inpatient Numerical Rating Scale (NRS) Pain Score	X	X	X	X
Medication Electronic Monitoring (MEMS) devices:		X	X	X
Defense and Veterans Pain Rating Scale (DVPRS)	X	X	X	X

Inpatient Sleep Actigraphy	X				l
Field notes and participant quotes	X	X	X	X	l
Participant Compensation	X	X		X	ı

Questionnaires/surveys and meetings with the Life Care Specialist will occur during scheduled telehealth appointments. No charges will be generated specifically relating to the research components.

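### Aim 1 does not force in each patient's starting value and does not say whether Visit 1 PROMIS is a baseline or an outcome

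*Combined protocol and SAP*

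**What the plan says.** Aim 1 (Statistical Analysis) fits a separate linear mixed model for each outcome, "adjusting for covariates (e.g., mental health history, BMI, surgery type, etc". The list is open-ended. LASSO selects from hundreds of record-based and patient-reported variables, and AIC judges the fit. No term is declared as forced in.

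The hypothesis is that the intervention arm has "lower average NRS pain scores and PROMIS scores postoperatively compared to participants in the control arm". The section does not list the visits that supply outcome rows and writes no arm-by-time term or visit contrast.

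In the visit schedule, the row "PROMIS: Pain Interference" is ticked at Visit 1 and at 2 weeks, 6 weeks and 3 months. So are Sleep Disturbance, Physical Function, NRS and DVPRS. Study Procedures/Assessments places the Visit 1 battery after allocation, during the hospital stay, with no timing relative to surgery or first LCS contact. Study design and methods places only the social determinants (SDOH) survey before randomization.

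Aim 2 uses the same selection approach, but fits separate models for inpatient MME/day and for MME/day at the follow-up points.

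The power statement reads "A sample of 200 provides 85% power", at an alpha of "0.05) to detect a difference as small as 0.5 in the mean pain score", "using repeated measures mixed effects modeling". It gives no SD, within-patient correlation or number of measurements.

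**The concern.** Two choices that affect the Aim 1 result are left to the analyst.

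- **Baseline.** A patient's own starting value is often among the strongest predictors of a repeated pain, sleep or function score. If selection drops it, the intervals widen for no benefit. If selection keeps it for some outcomes and not others, the adjusted models differ in a way fixed only after the data are seen.
- **Outcome rows.** A Visit 1 PROMIS form completed after surgery satisfies the word postoperative; one completed before surgery does not. The same form could be an outcome for one patient and not for another. Where it counts, the LCS may have had little time to act, and Pain Interference and Sleep Disturbance ask about the past seven days. Under a single arm term, such rows pull the estimated difference toward zero.

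**Working it through.** **Inputs from the documents.** 200 patients, "100 randomized into LCS intervention", so 100 per arm; difference 0.5 points; alpha 0.05; power 85%; three follow-up visits.

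**Assumptions.** Two-sided test; compound symmetry with correlation r of 0.3, 0.5 or 0.7; no dropout; the 85% refers to the mean of three follow-ups without baseline adjustment.

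**The plan's figure.** The 85% can be neither reproduced nor refuted, because the SD and correlation are not given. It corresponds to z = 1.960 + 1.036 = 2.996, which implies an SD of the analysed mean of 0.5 / (2.996 × √(2/100)) = 1.18. With three follow-ups the raw SD is 1.18 / √((1+2r)/3) = 1.62, 1.45 or 1.32 at r = 0.3, 0.5 or 0.7.

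**Variance of the patient-level summary, in units of the raw variance**

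- Follow-ups only: A = (1+2r)/3
- Follow-ups with baseline covariate: B = A − r²
- Visit 1 as a fourth outcome row under one arm term: C = (1+3r)/4. With no effect yet at Visit 1, the effect is 3/4 of 0.5 = 0.375.

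**Power.** With baseline, Φ(2.996 × √(A/B) − 1.96). Pooled, Φ(2.996 × 0.75 × √(A/C) − 1.96).

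| r | A | B | Variance cut | Power with baseline | C | Power if pooled |
|---|---|---|---|---|---|---|
| 0.3 | 0.533 | 0.443 | 17% | 90.8% | 0.475 | 66.3% |
| 0.5 | 0.667 | 0.417 | 38% | 96.6% | 0.625 | 64.1% |
| 0.7 | 0.800 | 0.310 | 61% | 99.8% | 0.775 | 62.7% |

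**Simulation check.** 300 trials with random-intercept models at r = 0.5, raw SD 1.445 and true effect −0.5:

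- follow-ups only: mean estimate −0.49, power 86%
- with baseline covariate: −0.49, 97%
- Visit 1 pooled: −0.37, 64%

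**Weaker baseline.** Let the baseline-to-follow-up correlation be b, separate from r. The variance cut is b²/A. For b = 0.1–0.2 and r = 0.3–0.7 it runs from 0.01/0.800 = 1.3% to 0.04/0.533 = 7.5%, and power from 85.4% to 87.6%. At b = 0.3 and r = 0.5 it is 0.09/0.667 = 13.5%, with power about 90%.

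**Larger SD.** At an assumed raw SD of 2.0 and r = 0.5, power is 58% with follow-ups only, 78% with baseline and 39% pooled. At SD 2.5 it is 41%, 59% and 27%.

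**Would LASSO keep the baseline anyway?** Simulated with 200 patients, the baseline plus 199 independent noise candidates, and a cross-validated penalty: the baseline was kept in 40 of 40 trials at each of r = 0.3, 0.5 and 0.7. This is an idealised case, with no missing data and no correlated proxies.

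**The case against.** The strongest reply is that the plan already allows for the baseline. The covariate list is open, patient-reported measures are in the candidate pool, and a strong predictor is what LASSO tends to keep, as the simulation shows. This largely stands. A reader might infer that Aims 1 and 2 ignore the starting value; the text does not support that. What it lacks is a commitment made before the data are seen. The 91%, 97% and over-99% figures measure the gain only against a model that drops the baseline.

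Second, the dilution is a worst case. It needs every Visit 1 to be post-operative, no effect yet, and one common arm term. An arm-by-time contrast or a constrained baseline model avoids it. Also, the 85% concerns a pain score, and inpatient NRS is charted daily while the LCS is active, so a zero inpatient effect on NRS is not established. These limits stand. The 75% is a bound, best read for the single Visit 1 PROMIS form.

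Third, a reader might extend the outcome-row point to Aim 2. It does not apply there, because inpatient and follow-up MME/day have separate models.

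Fourth, a reader might want the outcomes of every Aim 1 model limited to Visits 2 to 4. For NRS that would discard inpatient pain, which the Objectives list among the assessments.

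Fifth, the starting values are not all in hand. Inpatient MME is defined as an average over the stay, and neither NRS nor MME before randomization is scheduled. The figure "30% have previously used opioid medications for pain" in the Introduction and Background describes the hospital's trauma population and is not a trial variable. The SDOH survey covers prior substance use, which is not clearly prescribed opioids.

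**Conclusion.** The point holds for Aim 1, in a limited form: adjustment for the starting value is not pre-specified, and the role of Visit 1 PROMIS is not stated. It should be settled before analysis, but it does not show the trial's result to be biased.

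If LASSO would otherwise drop the baseline, forcing it in raises 85% to about 91%, 97% or over 99% at correlation 0.3, 0.5 or 0.7. The rise is only to about 85–88% if the baseline correlates 0.1–0.2 with follow-up, which is possible when a seven-day recall may straddle the injury. If LASSO keeps the baseline, the gain is pre-specification rather than power. Pooling Visit 1 costs at most a quarter of the estimate and leaves power at about 63–66%. All these figures rest on assumed compound symmetry and on taking the stated 85% as the anchor.

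For Aim 2, only the absence of a forced pre-randomization covariate carries over. No size is claimed for it.

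**What to change.** **Aim 1, PROMIS models (Pain Interference, Sleep Disturbance, Physical Function).** Name Visits 2, 3 and 4 as the outcome rows. Force in the Visit 1 score of the same scale, outside the LASSO. Require the Visit 1 battery to be completed before first LCS contact. State whether the arm effect is an average over the three visits or a visit-specific contrast.

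**Aim 1, NRS.** Analyse inpatient pain in its own model, separate from follow-up NRS. Force in a charted NRS dated before randomization where the EHR holds one. Do not adjust for whole-stay averages, which include LCS exposure and could remove part of the effect.

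**Aim 2.** Force in the prior substance-use item of the SDOH survey. Add pre-randomization MME only where a dated EHR extract supports it. Reconcile the timing of the survey: Study design and methods puts it before randomization, while Study Procedures/Assessments puts the tabulated battery, whose table includes it, after allocation.

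**Cost.** A few sentences in the SAP, an ordering rule at Visit 1, a dated EHR extraction, and simple imputation for missing baselines. No added visits or patients.

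### The LASSO covariate pool for Aims 1 and 2 is not limited to pre-randomisation values, so the arm coefficient may stop being the total effect of assignment

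*Combined protocol and SAP*

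**What the plan says.** Under Statistical Analysis, Aim 1 tests whether "participants in the intervention arm have lower average NRS pain scores and PROMIS scores postoperatively compared to participants in the control arm". The models are to be built by LASSO, chosen for its ability to "build the most predictive model with a large subset of covarying factors using a penalized approach", and judged on AIC. The candidates come from the "hundreds of data points collected from the electronic health records and the patient-reported outcomes collected per participant". The next sentence reads "The inclusion of these longitudinal measures makes it feasible to reduce statistical variation in the mixed effects models over time" and concludes that this isolates the effect of the intervention.

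Aim 2 carries the method over: "a systematic machine learning guided model construction approach will be used to also test the working hypothesis" about opioid use. The Power paragraph gives the selection step to software: the glmnet "package will be used to determine which variables should be included in the regression models using a LASSO approach", after which lme4 fits the final regressions.

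The only covariates named are examples in an open list: "adjusting for covariates (e.g., mental health history, BMI, surgery type, etc". The section also calls the candidates potential confounders. It gives no rule on when a candidate must have been recorded, and does not say that the arm term is exempt from selection.

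**The concern.** Randomisation protects the comparison of arms as assigned. Adjusting for variables fixed before assignment keeps that protection and usually gains precision. Adjusting for a variable measured afterwards, and changed by the intervention, removes part of the effect or distorts it.

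The pool as described contains such variables. The Objectives section expects the LCS to lower opioid use and pain scores and to improve understanding of risk. The visit schedule gives 11 instruments at visit 1 and again later. Four are Aim 1 outcomes (NRS and three PROMIS scales). The other seven are SF-36, PMQ, PDUQ, the PTSD screener, OLT, PAC-SYM and DVPRS. MME is also reviewed from the health record up to 3 months. A selector driven by prediction has no reason to leave DVPRS out of an NRS model.

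Both efficacy aims rest on the arm coefficient, and Study design and methods says the pilot is meant to supply effect sizes. A biased coefficient would pass straight into the design of a later trial.

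**Working it through.** **Does any section limit candidates by time?**

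- Statistical Analysis: no limit is stated for Aim 1 or Aim 2.
- Study Procedures/Assessments: the battery of measures is given after consent, enrolment and allocation, so a visit 1 value is not necessarily a pre-randomisation value.
- Study design and methods: the social determinants survey is given before randomisation. The schedule lists that survey at visit 1 too, so the two sections disagree on its order.
- Inpatient Pain and Opioid utilization: inpatient MME/day is averaged over the whole stay.
- Discharge data: pain and opioid values come from the last 24 hours before discharge.
- Introduction and Background: the intervention is introduced during the hospital stay. A line below the visit schedule places LCS meetings in telehealth appointments, so the exact start is not settled. The inpatient MME hypothesis in Aim 2 fits an inpatient start.

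So neither the pool nor the visit 1 label keeps arm-affected values out.

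**How large could the distortion be?** The plan gives no SD, within-patient correlation, number of repeated measures or sidedness, so its 85% power cannot be reproduced. It can be inverted to set a scale.

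Inputs from the plan: 100 per arm, alpha 0.05, 85% power "to detect a difference as small as 0.5 in the mean pain score between the intervention arm and the controls". Assumptions: two-sided test, one mean per participant, one follow-up covariate forced into the model.

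- Implied SE = 0.5 / (1.960 + 1.036) = 0.1669.
- Effective SD = 0.1669 / √(2/100) = 1.180.
- Standardised effect D = 0.5 / 1.180 = 0.424.

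(A one-sided test would imply SE 0.186 and SD 1.32.)

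Let r be the within-arm correlation of covariate and outcome, and f the covariate's standardised response to the arm divided by the outcome's. Then:

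- arm coefficient = 0.5 × (1 − r·f)
- SE = 0.1669 × √(1 − r²) × √(1 + (f·D)²/4)

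Example, f = 1 and r = 0.5: coefficient 0.5 × 0.5 = 0.25; SE = 0.1669 × 0.866 × 1.022 = 0.148; ratio 1.69; power 39%.

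| Response of covariate | r = 0.3 | r = 0.5 | r = 0.7 |
|---|---|---|---|
| Equal (f = 1) | 0.35, power 58% | 0.25, 39% | 0.15, 23% |
| Half (f = 0.5) | 0.425, 76% | 0.375, 73% | 0.325, 77% |
| None (f = 0) | 0.50, 88% | 0.50, 93% | 0.50, 99% |
| Half, opposite direction (f = −0.5) | 0.575 | 0.625 | 0.675 |

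A least-squares simulation with the covariate forced in (200 participants, 8,000 replicates) gave 0.350 / 0.251 / 0.151 with power 57% / 39% / 24% at f = 1, and 0.575 / 0.627 / 0.674 at f = −0.5, in agreement with the formulas.

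The table does not say how often LASSO would select such a covariate.

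**The case against.** The strongest reply is that this rests on silence. The section speaks of confounders, its examples are baseline in kind, and the longitudinal measures may be nothing more than the repeated outcomes that a mixed model uses anyway. That reading is fair. A reader might infer that the plan intends to adjust for follow-up measures; the documents do not support that. What remains is that the examples are open-ended, the sentence on longitudinal measures directly follows the description of the health-record and patient-reported pool, and no limit is written anywhere.

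A second reply is that the loss need not be large. That also stands. With half the response, power stays between 73% and 77%. With no response there is no bias, and precision improves, which is the gain the plan seeks. The equal-response row is the most severe of the cases shown. A reader might infer that the trial's estimate will be biased towards zero; neither the occurrence nor the direction of bias can be known from the documents.

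A third reply concerns the arm term. A reader might infer that its reported coefficient is shrunk by the penalty. It is not, because glmnet only selects and lme4 refits. The remaining risk is that the arm term is dropped at selection, which the plan's purpose makes unlikely but its wording does not exclude.

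**Conclusion.** The concern holds in conditional form and should be fixed. Following the text as written can put arm-affected variables into the main models of both efficacy aims, and the arm coefficient would then be an unplanned conditional contrast. The stated power for a 0.5 difference would not describe that contrast.

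In the illustration, a true 0.5 could appear as anything from 0.15 to 0.675. That range depends on the assumed correlations and responses, a two-sided test, a single participant mean and a single covariate, whereas the plan uses repeated-measures models with many candidates. It shows direction and possible scale and is not a forecast for this trial. The absence of a timing rule is certain; its consequence depends on what is selected.

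**What to change.** 1. In Statistical Analysis, for Aims 1 and 2, limit LASSO candidates for the main models to variables recorded before randomisation, or characteristics fixed by then that assignment cannot affect. Apply this one timing rule throughout, in place of the visit 1 label. Surgery type qualifies where the procedure was already set at randomisation.
2. Use follow-up measures, whole-stay averages and discharge values only as outcomes. Label any model that adjusts for them as exploratory.
3. State that the arm term stays in every model, unpenalised.
4. Reconcile Study design and methods with Study Procedures/Assessments so that every measure used as a baseline covariate, including the baseline value of the outcome where one exists, is completed before allocation.

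The cost is SAP wording plus a protocol change that fixes the order of the baseline battery; wording alone is not enough. Staff must finish those measures before allocating, and the main model gives up some exploratory covariate screening. No new data items are needed, and LASSO over baseline candidates may stay.
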